Administrative data consist of employment records and medical and pharmaceutical claims data. Employment records are available for all employees across treatment and control worksites (both primary and secondary controls). Medical and pharmaceutical claims data are available through Cigna for BJ's employees who are insured through a Cigna plan. In cross-section, approximately 37 percent of all BJ's employees were insured through Cigna during June 2016 (the midpoint of phase 2). Of note, BJ's as an organization is self-insured (i.e. it bears risk of health care spending of its enrolled members), with Cigna as the administrator of its health plans. We used all administrative data available for the entire study period.

A1. Employment records

BJ's provided us with data from their earnings database, which includes data elements that we use both to define our sample (based on hire and termination dates) and to measure key outcomes, such as absenteeism and performance reviews. Information included:

- **Dates and location of employment actions:** Dates and sites of hire, rehire, termination, transfer, and performance review. These data capture employment history across clubs. A small proportion of employees (4.5%) appeared in more than 1 worksite during the study period. We defined these workers' treatment or control assignment using the randomized assignment of their initial worksite, as the decision to leave (or stay) at a worksite could be endogenous. Most employees have one performance review per calendar year.
- **Demographic characteristics:** Characteristics of the working population include age, sex, and race. These are discussed in greater in the section on Analysis below. Worksite level analyses, as described below, were augmented using 2015 estimates of county-level demographic characteristics from the U.S. Census Bureau matched to the locations of each worksite.
- **Employment characteristics:** Characteristics of an individual's job include type of hired arrangement (full time salaried, full time hourly, and part time hourly) and type of job. The types of jobs were grouped into three categories: sales, non-sales (including laborers and helpers, operatives, and service workers), and other (including administrative support, craft workers, and first/mid-level office professionals).

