In this representative estimating equation, Y_{ijt} denotes an outcome of interest, such as medical spending, for individual i who is employed in worksite j at time t . $TREATMENT_{jt}$ is a binary indicator of whether the individual's worksite was randomized into treatment or control. We assigned each individual to the worksite at which he or she was employed when the treatment began in January 2015. $TIME_WORKED_{ijt}$ is the share of total available work hours in the study period that the individual actually worked; it is expressed in percentage terms. The effect of randomization to a treatment worksite is allowed to vary based on exposure to the treatment (measured via time worked during the treatment period). The treatment effect is captured by $\beta_1 + \beta_3 * Exposure$. The average effect of randomization into the treatment group can be summarized by assessing this at the average level of exposure. While we will produce estimates of the average effect of randomization into treatment, as captured in the layout of Tables 3-6, we will additionally show results for both β_1 and β_3 for each of our results in a set of parallel tables.

X_{ijt} represents a vector of covariates that may help improve precision as well as account for chance differences in characteristics between treatment and control groups, including:

- Age indicators: <20 years (omitted), 20-29, 30-39, 40-49, 50-59, and 60 and greater.
- Sex indicator: male (omitted), female
- Age-sex interactions
- Race: white (omitted), black, Hispanic, and other
- Employment characteristics (measured at baseline for the stably employed subsample):
 - Part-time (omitted), full-time
 - Salaried (omitted), hourly
 - Sales worker (omitted), non-sales worker, and other worker.

ε_{ijt} is the idiosyncratic error term. The models are weighted using the sample weights described above. Standard errors were clustered at the worksite level.

B. Local average treatment effect (LATE)

While our ITT analysis explores the effect of being randomized into a treatment worksite, a related but distinct question is: what is the effect of participating in the wellness program on the outcomes of interest? The answer to this second question will be different if not all employees in treatment worksites elect to participate. Because the choice to participate in the program is endogenous, simply including participation as a right-hand side variable may produce biased

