The key identifying assumption is that the only mechanism through which being employed in a treatment worksite affects outcomes is through the availability of the wellness program. There are two threats to this assumption. First, to the extent that covariates were not balanced at baseline and those covariates affect the outcomes of interest, that imbalance could bias our estimates. We control for observed covariates and apply weights to balance covariates between treatment and control. Despite these adjustments, unobserved covariates might still be imbalanced.

Second, to the extent that the wellness program affected hiring or tenure of employees, their presence in the data set may be endogenously determined. We address the issue of endogenous entry by pre-specifying a subsample of those who were already employed at the time the intervention began. We defined this more restrictive “stable employment” subsample as comprising employees who had worked continuously for 13 weeks prior to the wellness program. This comes at a cost of reducing the overall sample size. Our goal in choosing the definition for this subsample was to balance the costs and benefits, as detailed in Appendix 2.

In this stably employed subsample, however, exit from the firm's workforce is still potentially endogenous. We deal with this concern in two ways. First, we will test balance on exit between treatment worksites vs. from control worksites overall and for subgroups. Indeed, tenure and time worked are among our primary outcomes. To the extent that we observe any unbalanced exit, we will perform a bounding exercise (assuming that those who exited have outcomes working against any observed effects of the intervention).

D. Subgroup analyses

We pre-specified three subgroup analyses. We selected these subgroups based on differences in key outcomes within the control group for those with different baseline characteristics, such as differences in medical spending by age or in reported exercise by sex (**Table 11**).

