Notes: Table reports the coefficient on TREATMENT from estimating equation (1) by OLS (column 2), and the coefficient on PARTICIPATION from estimating equation (2) by IV (column 3). Standard errors are listed in parentheses. Column 1 reports the mean of each employment outcome in the control group for each sample (with standard deviation in parentheses, followed by the number of observations for each outcome). All regressions will include demographic and employment controls (age, sex, age-sex interactions, race/ethnicity, Cigna coverage status, full-time status, paid hourly status, and job category) and cluster standard errors at the worksite (for employee-level regressions). Employee-level and stably employed subsample control means are weighted by a weight that balances treatment and control on demographic characteristics. Worksite-level control means are not traditionally weighted: individual-level records are collapsed at the worksite-level and weighted by the total number of hours worked at each worksite. For worksite level results on tenure, the outcome was defined as the percent of total days at the worksite during the study period that was worked by employees at the worksite.

§ Tenure was defined as the number of days worked during the treatment period for the employee-level mean and stably employed subsample mean; it was defined as the percent of the entire treatment period worked by employees in the worksite-level mean.

Table 4: Impact on Medical & Pharmaceutical Spending and Utilization

	Employee-level			Stably Employed Subsample			Worksite-level (per 2000 work hours)		
	Mean in Control Group (1)	Reduced Form (Linear) (2)	2SLS (Linear) (3)	Mean in Control Group (1)	Reduced Form (Linear) (2)	2SLS (Linear) (3)	Mean in Control Group (1)	Reduced Form (Linear) (2)	2SLS (Linear) (3)
Medical Spending									
Total Spending	4800.57 (18559.82)			4721.85 (19056.92)			5044.74 (2994.54)		
Medical Utilization									
Number of Office visits	3.90 (4.47)			3.95 (4.33)			4.21 (0.93)		
Number of Hospitalizations	0.09 (0.40)			0.08 (0.36)			0.08 (0.05)		
Number of ER Visits	0.28 (0.75)			0.26 (0.61)			0.27 (0.11)		
Pharmaceutical Spending									
Total Spending	1237.60 (6921.32)			1227.32 (7115.67)			1317.72 (1145.17)		
Pharmaceutical Utilization									
Number of Distinct Medications	5.49 (6.44)			5.91 (6.54)			6.00 (1.30)		
Total Medication Months	11.20 (19.31)			11.41 (19.37)			12.39 (4.38)		
N	7,174			5,779			135		

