Appendix 2. Determination of the Stably Employed Subsample

[figure not shown]
We conducted an analysis of the duration of employment (tenure), which informed our definition of the pre-specified stably employed subsample. This analysis of tenure is described below.

Figure 1A looks at a number of scenarios where we take samples of treatment (T) and control (C) workers who were employed for varying numbers of consecutive weeks starting on 1/1/2014. In each scenario, we follow the samples of workers until they reach 1/1/2015 and look at how many of them are still employed. To be precise, for each restriction criterion of the number of consecutive weeks worked starting 1/1/2014 (X axis), the height of the dark blue bar (C 14) depicts the total number of control workers in the sample and the height of the light blue bar (C 15) depicts the total number of control workers who were still working on 1/1/2015. Analogously, the height of the black bar (T 14) represents treatment workers who started in the sample on 1/1/2014 and the height of the gray bar (T 15) represents treatment workers who were still working on 1/1/2015. Of note, the bars are overlapping for each X (i.e. they are not stacked; rather they all originate at 0). The solid and dotted lines merely reflect the percentages of C and T employees, respectively, who were still working at BJ's on 1/1/2015 (i.e. light blue bar divided by dark blue bar, gray bar divided by black bar).

Thus, for example, the interpretation of the bar when X=17 is as follows. There were about 10,000 employees in control worksites who were employed at BJ’s on 1/1/2014 and who worked through the first 17 weeks of 2014 (dark blue bar). Among these employees, about 79% (or about 7,900) were still working on 1/1/2015 (light blue bar). The same retention of 79% was found among employees in treatment worksites—calculated using the gray (numerator) and black (denominator) bars. The bar originating at X=0 represents the case of no sample restrictions (i.e. all employees in the data).

[figure not shown]

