Similarly, Figure 1B shows a similar analysis when we extend the definition of retention to 12/1/2015. This graph contains only control worksite employees, because tenure itself may be affected by the wellness program and is an outcome we will examine formally in the analysis. To extend the above example of interpretation, of the 10,000 employees in control worksites who were employed through the first 17 weeks of 2014, about 64% were still employed on 12/1/2015. This decrease is from 79% at the beginning of 2015, implying that 15% of the sample (79% – 64% = 15%) were “lost” from the sample (e.g. terminated, left BJ’s) during the first 11 months of 2015.

Analyzing samples defined with respect to 3/1/2015 (start of the first module): Figure 2 takes a different approach to looking at tenure. It looks at retention for samples of employees defined based on the number of continuous weeks worked immediately *before* the wellness treatment

launched (i.e. defined by counting backwards from 3/1/2015). Retention here is still defined as appearing in 12/1/2015. As above the figure contains only employees from control worksites.

As an example of interpretation, there were about 13,500 employees in control worksites who worked during the 13 continuous weeks (~3 months) before the start of the wellness program (counting back from 3/1/2015 -- i.e. Feb '15, Jan '15, and Dec '14). Among these 13,500 employees, about 10,000 remained actively working on 12/1/2015. This amounts to about a 75% retention rate.

We examined the rate of decline of this sample of employees among control worksites throughout the treatment. Figure 3 shows the rate of decline of the above control sample (those who worked for the 13 consecutive weeks leading up to the start of the treatment (3/1/2015), and illustrates the decline in the number and percent of this sample through 2017. The X axis shows the months elapsed since start of the treatment (0 is the end of February 2015, while 34 is the end of December 2017). This graph shows a smooth decline in the sample of employees to reach 51% by the end of December 2017

Figure 3. Tenure Analysis (Control TMs)

Sample: C TMs employed during the 13 weeks before the intervention

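### For the stably employed subsample, the tenure model and its balance table leave out length of service at program start, a pre-treatment value the trial holds; the gain from adding it is modest

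*Combined protocol and SAP*

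**What the plan says.** Section VI.C states that "tenure and time worked are among our primary outcomes". Section VI.A gives X two purposes, precision and chance imbalance, calling it "a vector of covariates that may help improve precision as well as account for chance differences in characteristics". The listed items are age bands, sex, their interactions, race, and three job descriptors: full or part time, salaried or hourly, and job category. For the subsample at issue these are baseline values: "Employment characteristics (measured at baseline for the stably employed subsample".

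The list in Section VI.A is introduced as examples, so X is formally open. The note to Table 3, which governs the tenure model, is more definite: "All regressions will include demographic and employment controls (age, sex, age-sex interactions, race/ethnicity, Cigna coverage status, full-time status, paid hourly status, and job category". Length of service appears in neither place.

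The data exist. Section IV.A1 lists "Dates and sites of hire, rehire, termination, transfer, and performance review" among the employment records and builds tenure from the hire date, using first appearance in the database where no hire date is recorded. Table 8 Panel D, the balance table for this subsample, covers demographics, worker type, pay, standard hours, job category, insurance and medical spending, but not length of service.

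Appendix 2 reports retention among control employees in order to choose the 13-week rule. For about 10,000 employed on 1/1/2014 and through the next 17 weeks: "Among these employees, about 79% (or about 7,900) were still working on 1/1/2015", and "about 64% were still employed on 12/1/2015". For the 13-week sample of about 13,500: "Among these 13,500 employees, about 10,000 remained actively working on 12/1/2015".

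**The concern.** Prior service is a natural predictor of who stays. In this subsample it is fixed before the program starts, so adjusting for it cannot introduce post-treatment bias. The plan already takes other job characteristics at baseline here and leaves this one out.

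Two things are at stake. The first is precision on a primary outcome. The second is chance imbalance in service mix between 25 treatment and 135 control worksites. The weights balance only age, sex and race (Section V.B). Chance differences did occur in this randomization: race differed at p<0.001 before weighting (Table 8 Panel A.1). Service mix matters for one decision in particular. Section VI.C makes the bounding exercise depend on whether exit is unbalanced, and it names no covariates for that test. A difference in service mix could trigger or hide that step.

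**Working it through.** **Reproducing the plan's figures.** 10,000/13,500 = 74.1%, against about 75% stated in Appendix 2. 0.79 × 10,000 = 7,900, and 79% − 64% = 15%, both as stated.

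**Which tenure outcome Table 3 reports.** Take a piecewise-exponential curve through 74.1% or 75% at month 9 and 51% at month 34 (Appendix 2).
- Monthly exit hazards: h₁ = −ln S(9)/9 = 0.033 or 0.032, and h₂ = −ln(0.51/S(9))/25 = 0.015.
- Mean days = 30.44 × [(1−S(9))/h₁ + S(9)(1−e^(−25h₂))/h₂] + 59 days for January-February 2015 = 766 to 771.
- Table 3 gives 786.57, so it reports days within the treatment window.
- The hazard halves after month 9. That fits shorter-service staff leaving first, though other differences between employees could produce the same pattern.

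**Service gradient in controls.**
1. Long-service cohort: 7,900 on 1/1/2015 and 0.64 × 10,000 = 6,400 on 12/1/2015. At a constant hazard, the number on 3/1/2015 is 7,900 × (6,400/7,900)^(2/11) = 7,603.
2. Nine-month retention, long service: 6,400/7,603 = 84%.
3. The rest: 13,500 − 7,603 = 5,897, of whom 10,000 − 6,400 = 3,600 remain: 61%.
4. R² = w(1−w)(p_L − p_S)²/[p(1−p)], with w = 7,603/13,500 = 0.563 and p = 0.741: 0.563 × 0.437 × 0.231²/(0.741 × 0.259) = 0.068.

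This assumes that the long-service cohort lies inside the 13,500. Varying the interpolation and rounding gives:

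| 13-week sample, start → retained | Long-service on 3/1/2015 | Long | Rest | Exit ratio | R² |
|---|---|---|---|---|---|
| 13,500 → 10,000 | 7,603 (constant hazard) | 84% | 61% | 2.5 | 0.068 |
| 13,500 → 10,000 | 7,900 (no one left Jan-Feb) | 81% | 64% | 1.9 | 0.035 |
| 13,500 → 10,000 | 7,347 (7% left Jan-Feb) | 87% | 59% | 3.2 | 0.106 |
| 13,500 → 10,125 | 7,900 | 81% | 67% | 1.8 | 0.027 |
| 13,000 → 9,630 | 7,347 | 87% | 57% | 3.3 | 0.115 |

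**From retention to days.** Give the two groups Weibull exit times with a common shape, set so that the mixture reaches 51% at month 34 (shape 0.65). Simulated mean days are 871 and 593, with overall SD 407. R² = 0.563 × 0.437 × (871 − 593)²/407² = about 0.115. The simulated mean (750) and SD (407) are near, but not equal to, Table 3's 786.57 and 376.96.

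**Precision.** SE = SD × √[ICC(1/25 + 1/135) + (1−ICC)(1−R²)(1/2,344 + 1/13,000)], with SD = 376.96 (Table 3) and the sample sizes in Table 8 Panel D. The minimum detectable difference (MDD) is SE × (1.96 + 0.84). Two-sided 5%, 80% power and the ICCs are assumptions; the covariate is taken to explain only within-worksite variance.

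| Assumed ICC | MDD, R² = 0 (days) | R² = 0.115 | R² = 0.30 |
|---|---|---|---|
| 0 | 23.7 | 22.3 (6% smaller) | 19.8 |
| 0.01 | 32.9 | 32.0 (3%) | 30.3 |
| 0.05 | 56.4 | 55.8 (1%) | 54.9 |

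**Likely size of a chance imbalance.** The SE of the between-arm difference in long-service share is √{0.563 × 0.437 × [ICC(1/25 + 1/135) + (1−ICC)(1/2,344 + 1/13,000)]} = 1.5, 2.6 and 3.6 points at assumed ICCs of 0.01, 0.05 and 0.10. Times the 0.231 gap, a one-SE imbalance moves retention by about 0.4 to 0.8 points.

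**The case against.** The strongest reply is that this is an optional covariate with a small return. Much of that stands.

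- A reader might infer that Appendix 2 demonstrates length of service to be a strong predictor, stronger than most listed covariates. It does not. The gradient comes from subtracting one rounded cohort from another. The documents give no retention by age, full-time status, pay type or job category, so no ranking is possible. X already holds variables that plausibly overlap with service, and only the increment counts.
- The split is not purely long against short service. Staff present in January 2014 who missed the 17-week condition, or who left and were rehired, can fall into the second group. Being in post on 1/1/2015 does not by itself prove membership of the 13-week sample. These points weaken the gradient without removing it: with no January-February exits it is still 81% against 64%.
- A reader might also infer a biased estimate, for example a false difference of 2.3 points from a 10-point gap in long-service share. No such gap is reported, and 10 points is about 6, 4 and 3 standard errors at the ICCs above. Under randomization, ordinary chance variation is already reflected in the clustered standard errors. Appendix 2 found 79% retention to 1/1/2015 in both arms. That is mildly reassuring, but it describes one cohort's 2014 retention, not the service mix of the subsample.
- Equation (1) conditions on TIME_WORKED, which is measured after baseline and is close to the tenure outcome itself. While it stays in the tenure model, adding service would change little. This is right, and it shapes the fix. It does not clearly reach the exit-balance test, which the plan does not tie to equation (1).

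**Conclusion.** The point holds as a minor one. Tenure is among the primary outcomes, length of service is absent from both covariate lists and from Panel D, and the variable is held and fixed before treatment for this subsample. Appendix 2's figures imply a real but unadjusted gradient, roughly 81-84% against 61-64% nine-month retention, with R² of about 0.03-0.12. This rests on rounded counts, on the nesting assumption and on interpolation over two months. The likely precision gain is 1-6% in the MDD at R² of about 0.11. It would reach 16% only if the covariate explained an assumed 30% of the variance and there were no clustering. The increment over the existing covariates cannot be computed from the documents.

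The rest of the value is insurance: a known predictor of exit would be checked and adjusted for before the exit comparison decides whether bounding is needed. The documents do not support a claim of existing bias or imbalance. They give no randomization date, so the covariate should be called pre-treatment rather than pre-randomization.

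**What to change.** For the stably employed subsample:
1. Add length of service at the program's start to the covariates of the tenure model and of the exit-balance test. Take it from the hire date, in bands (for example under 6 months, 6-12 months, 1-3 years, 3-10 years, over 10 years), with a flag where first database appearance was substituted. Fix the reference date: Appendix 2 counts back from 3/1/2015, whereas the treatment period begins in January 2015.
2. Add the same variable to Table 8 Panel D.
3. For tenure, use a model without TIME_WORKED, in the form of equation (7). Keep the balance weights: Section VI.F describes the phase 1 model as weighting by exposure, which for this outcome would nearly be weighting by the outcome.
4. Use one definition of tenure. Section IV.A1 runs from hire to latest termination; the Table 3 note counts days in the treatment period. Under the first, prior service is part of the outcome and omitting it would cost much more precision.

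Extending the covariate to absenteeism and performance is optional, since no figures in the plan bear on it. The cost is SAP wording, a few degrees of freedom and some truncated service values where hire dates were substituted. The plan says that no post-treatment outcomes had been compared by arm when it was written, so the covariate could have been pre-specified at that stage.
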